## Data Collection Measures:

The baseline characteristics questionnaire used in the proposed study has been thoroughly evaluated with over 1000 subjects (over 50% with HIV). The current study team has used this questionnaire with study participants in the Moore Clinic. Questions have been added or removed as applicable to this study and patient population. If a participant reports any alcohol use in the past 6 months on the questionnaire, the Alcohol Use Disorders Identification Test (AUDIT) will also be administered. The AUDIT consists of 10 items about recent alcohol use, alcohol dependence, symptoms, and alcohol-related problems. It was first developed in 1989 and has been validated in diverse international samples. The internal consistency reliability has been reported at 0.83 to the mid-0.90s. In a primary care setting, the AUDIT is intended to be administered by a nurse or social worker, and will be administered by a registered nurse in the proposed study. The research nurse case manager will counsel participants about alcohol use according to the recommended actions of the World Health Organization based on the individual AUDIT score. Participants scoring in Zone IV, suggesting alcohol dependence, will be referred to their Bartlett Specialty Practice social worker to discuss further counseling and treatment options.

The 19-item Brief Hepatitis C Knowledge Scale (Cronbach's  $\alpha=0.87$ ) will also be administered to measure baseline HCV knowledge. The Brief HCV Knowledge Scale includes a comprehensive list of items in its single factor that address the main aspects of HCV knowledge: prevention, risk reduction, transmission, and treatment. It was designed and tested on a diverse sample of patients, health care workers, and students with different socioeconomic and demographic backgrounds. It uses a simple true/false/don't know scoring system.

Depression can be associated with engagement in health services; therefore, the Patient Health Questionnaire (PHQ-9) will be administered. The PHQ-9 will be scored immediately. Participants scoring 10-19, indicating moderate depression, will be referred to their primary care provider for further follow up. Those

Date: May 8, 2017

Principal Investigator: [name], MPH, NP

Application Number: IRB00081068

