with scores of 20 or greater (severe) will be referred to their primary provider, or, if the primary provider is not available, the covering urgent provider of the day, for further evaluation before the study is continued.

All questions in the protocol will be asked in a private area and can be administered by a study team member in 30-45 minutes. In addition to the subject questionnaire, each instrument contains a section for the research team to interrogate the patient's medical record to verify specific pieces of the medical history. These variables of interest include:

- CD4+ T cell count
- HIV viral load
- Prescribed HIV treatment
- Year of HCV diagnosis
- HCV RNA
- Fibrosis score
- HCV genotype
- HCV referral history
- HCV appointment history
- HCV treatment initiation barriers
- Hopkins appointment no-show rate

In addition to baseline and outcome data collection, monthly activity logs will be collected for each study participant, independent of allocated study arm. The type, quantity, and content of all encounters with a study participant in the Johns Hopkins system will be recorded each month, including nurse visits. This will define usual care for Bartlett Specialty Practice patients. The type, quantity, and content of all Care2Cure study visits will also be recorded to define the dose of the intervention. Data will be collected from the study participant's Epic record and the interventionist's notes.

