### **Nurse Case Management Intervention Phase 1 – Linking to Care:**

Following informed consent, randomization, and completion of the baseline questionnaire, participants allocated to the intervention group will receive the first phase of the nurse case management (NCM) intervention (Table 1). This phase of the intervention will increase linkage to HCV care through NCM consisting of nurse-initiated referral, strengths-based HCV education, patient navigation, and HCV appointment reminders. The research nurse case manager will initiate an HCV referral for participants randomized to the

Date: May 8, 2017

Principal Investigator: [name], MPH, NP

Application Number: IRB00081068

intervention group via the electronic health record. This will send a cue to the HIV provider to approve the referral and minimize the barrier of non-referral by the provider. Participants will then receive brief strengths-based HCV education. Strengths-based education can improve knowledge and motivation to achieve health-related goals in PLWH. The research nurse case manager will help participants identify their strengths within the context of engaging in HCV care, including social support and engagement in HIV primary care. HCV education will include transmission, symptoms, treatment, and risk reduction. Participants will also identify barriers to linkage to care and form a plan with the research nurse case manager to minimize these barriers; this may include referrals to benefits counseling, substance use, mental health services, and the Johns Hopkins “Cure Club” HCV support group.

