## 7. Study Statistics

### Analysis:

Data will be cleaned and efforts made to minimize the effects of missing data. All provider visits at Johns Hopkins are registered in the electronic medical record, so absence of a registered appointment during the study period will be considered non-attendance for the primary outcome variable. A computer-based data collection method will be used for data collection of independent variables in attempt to minimize missing data. Exploratory and descriptive analysis will be completed for all study variables. Variables will be tested for normality and examined with means and standard deviations or medians and interquartile ranges accordingly. Baseline characteristics comparing the two groups (usual care vs. intervention) will be assessed. Any differences between the groups will be adjusted for in further analysis. The significance level will be set at 0.05. All tests will be two-tailed and analyzed by intention-to-treat.

**Primary Outcome:** The primary outcome is linkage to care, measured by attendance at the Viral Hepatitis Center (either traditional care or an HCV-treating clinical trial) within 60 days of randomization (yes/no). This hypothesis will be tested using a two-sample z-test for the difference in independent proportions comparing the intervention to usual care groups.

**Secondary Outcome:** The secondary outcome is time to HCV treatment initiation, measured by the number of days from randomization to the date HCV treatment is initiated according to the medical record. Kaplan Meier estimates will be conducted to compare time to HCV treatment initiation between participants in the intervention group and the usual care group, and a log-rank test will be used to test the difference. Covariates (age, sex, race/ethnicity, HCV knowledge, substance use, fibrosis score, CD4+ T cell count, HIV viral load, care giving responsibilities, and participation in Cure Club) will be included in the Cox regression model. To account for a time to treatment initiation greater than the observed time period of 6 months, right censoring will be implemented for participants who have not initiated HCV treatment at the end of the 6-month period.

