**Exploratory Analysis:** Binary logistic regression will be used to determine an effect on linkage to care controlling for differences in age, sex, race/ethnicity, HCV knowledge, substance use, fibrosis score, CD4+ T cell count, HIV viral load, care giving responsibilities, and participation in Cure Club. A correlation matrix will be used to assess multicollinearity of the independent variables, and those with a correlation of greater than 0.6 will be considered for removal from the model. The remaining covariates will be entered into the model first, followed by the independent variable of interest (intervention vs. usual care). To evaluate how much predictive

Date: May 8, 2017

Principal Investigator: [name], MPH, NP

Application Number: IRB00081068

power was added to the model by adding the variable(s) of interest, the change in likelihood ratio test will be evaluated.

**Exit Interview:** Descriptive statistics will be used to examine the overall satisfaction of participants in the study. One-way frequency analysis will describe the intervention group's perceptions of the intervention and the interventionist to inform future studies. Participant responses to the barriers to linking to HCV care and initiating therapy will be grouped into categories and compared between the intervention and control group using a categorical Chi-Square test to determine if there is any difference in quantity and category of barriers to accessing care.

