### **Sample Size Justification:**

Currently, 40% of new Viral Hepatitis Clinic appointments are attended by patients. Based on prior studies testing the intervention components in similar populations, including persons living with HIV and/or substance use disorders, it is expected that the intervention will improve the primary outcome of linkage to care by 18-30%. Although the effect size is not known in the context of HCV, we estimate an improvement in linkage of 20% (i.e., 60% attendance [0.60] in the NCM group compared to 40% attendance [0.40] in the usual care group) based on these prior studies. Using these figures and a two-tailed test with an alpha of 0.05, a conservative estimate of the total sample size required to achieve 80% power is 97 per group, or a total of 194 participants (G\*Power 3.1.9.2). With a sample size of 100 participants in each group, there should be an adequate number of participants to detect a difference in proportion of linkage to care for the primary aim.

For Phase 2, participants with successful linkage to clinical care from Phase 1 (those who attend  $\geq 1$  appointment at the Viral Hepatitis Clinic within 60 days) will be included. Therefore, the eligible sample size will be less than 40-60% of the original sample size because a linkage to care proportion of 0.40-0.60 is expected, and some participants will link to a clinical trial and not be included in this outcome. This is a secondary outcome and estimated effect size is unknown. However, with 100 participants in this group (half of the total sample size), we will have 90% power to detect a hazard ratio of 2.

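### Cure Club participation is an undated covariate in the Cox and logistic models, although the only route into it that the plan describes is a post-randomisation referral in the intervention arm

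*Combined protocol and SAP*

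**What the plan says.** Section 7 (Study Statistics, Analysis) lists ten covariates for the Cox model of time to HCV treatment initiation. The list ends: "care giving responsibilities, and participation in Cure Club) will be included in the Cox regression model". The exploratory logistic model for linkage has the same ten, ending "HIV viral load, care giving responsibilities, and participation in Cure Club". Neither list dates the Cure Club item.

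The logistic model also fixes the order of entry: "The remaining covariates will be entered into the model first, followed by the independent variable of interest (intervention vs. usual care"). The contribution of arm is then judged by the change in the likelihood ratio.

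Outside Section 7, Cure Club appears once, under Nurse Case Management Intervention Phase 1. It is one of several referrals that a participant's barrier plan may contain: "mental health services, and the Johns Hopkins “Cure Club” HCV support group". On who receives Phase 1 and when, the same section says: "Following informed consent, randomization, and completion of the baseline questionnaire, participants allocated to the intervention group will receive the first phase".

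The Data Collection Measures section does not name Cure Club among the baseline instruments or the record-abstraction variables. The description of enhanced usual care does not mention it either. HCV knowledge, from the same covariate list, is dated: its scale "will also be administered to measure baseline HCV knowledge". A later source may exist for both arms: "The type, quantity, and content of all encounters with a study participant in the Johns Hopkins system will be recorded each month". Whether a support group counts as an encounter is not stated.

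**The concern.** A covariate in a model for a randomised effect should be fixed before allocation. On the only description the plan gives, joining Cure Club follows allocation and may be caused by it. Adjusting for it then removes whatever part of the effect runs through Cure Club. It also compares joiners with joiners and non-joiners with non-joiners, and these groups need no longer be balanced by randomisation. The arm coefficient is then not the effect of assignment, although Section 7 commits the analysis to intention-to-treat.

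The Cox model has a second problem. If participation is coded as a fixed yes/no from follow-up data, people who start treatment late have had longer to join. Joining then looks as if it delays treatment even when it does nothing, and the arm estimate moves with it.

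The estimates at stake are the adjusted hazard ratio and the exploratory odds ratio. The logistic model is more than descriptive, because its stated purpose includes determining an effect on linkage and it tests what arm adds after the covariates. Aim 3, on characteristics associated with uptake of HCV care, could also report a misleading association for Cure Club itself.

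**Working it through.** **Inputs from the plan.** Linkage of 40% against 60% (Sample Size Justification), 1:1 allocation, censoring at 6 months, and a hazard ratio of 2 as the secondary planning value. The plan's sample size reproduces: [1.96·√(2·0.5·0.5) + 0.8416·√(0.24 + 0.24)]² / 0.20² = (1.3859 + 0.5831)² / 0.04 = 96.9, so 97 per group. That figure is not in dispute and does not depend on the covariate.

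**Assumed inputs.** The documents give no Cure Club uptake, no effect of joining and no treatment-start rate. Control uptake is set at 5% throughout; the other values are varied.

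**Logistic model.** Let u₀ and u₁ be uptake in control and intervention, θ the odds ratio for joining, and o₀ and o₁ the odds of linkage among non-joiners. Solve

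- (1 − u₀)·o₀/(1 + o₀) + u₀·θo₀/(1 + θo₀) = 0.40
- (1 − u₁)·o₁/(1 + o₁) + u₁·θo₁/(1 + θo₁) = 0.60

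The adjusted odds ratio is o₁/o₀. The unadjusted one is (0.60/0.40)/(0.40/0.60) = 2.25.

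Example with u₁ = 25% and θ = 2:

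- Control: o₀ = 0.643, since 0.95·0.3914 + 0.05·0.5626 = 0.400.
- Intervention: o₁ = 1.276, since 0.75·0.5605 + 0.25·0.7184 = 0.600.
- Adjusted odds ratio: 1.276/0.643 = 1.98.

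| Uptake, intervention vs control | Joining OR | Adjusted arm OR | Change from 2.25 |
|---|---|---|---|
| 5% vs 5% | 2 to 3 | 2.26 to 2.27 | under +1% |
| 10% vs 5% | 2 | 2.19 | −3% |
| 25% vs 5% | 2 | 1.98 | −12% |
| 25% vs 5% | 3 | 1.86 | −17% |
| 25% vs 5% | 0.5 (joiners face more barriers) | 2.61 | +16% |

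The first row is what a baseline measure would look like: equal uptake and no loss. The other rows treat every joiner as having joined in time to affect linkage within 60 days, so they lean towards a larger shift.

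**Cox model, all randomised participants.** Control hazard is constant at −ln(1 − p)/180 per day, with p = 20% or 40% starting treatment by 6 months (0.00124 and 0.00284). The arm hazard ratio is 2 with Cure Club status held fixed. Joining times are uniform over 180 days, the hazard is multiplied by the joining hazard ratio after joining, and follow-up is censored at 180 days. The large-sample estimates with and without a fixed yes/no term solve the expected score equations on a 0.1-day grid. Ranges cover the two values of p.

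| How joining is counted | Joining HR | Intervention uptake | Arm HR without term | Arm HR with term |
|---|---|---|---|---|
| (a) any time in 6 months | 2 | 10% | 2.03–2.04 | 2.00 |
| (a) any time in 6 months | 2 | 25% | 2.13–2.16 | 2.00 |
| (b) only before treatment start | 1 | 10% | 2.00 | 2.04–2.05 |
| (b) only before treatment start | 1 | 25% | 2.00 | 2.21–2.24 |

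Simulation with 300,000 per arm agrees. Case (a) at 10% uptake goes from 2.04 to 2.01 and from 2.02 to 1.99. Case (b) at 25% goes from 2.01 to 2.25 and from 2.00 to 2.20. In case (b) the fitted Cure Club hazard ratio is about 0.44 to 0.48, although joining has no effect in the model. That is the extra time late starters have to join.

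**The case against.** The defect is conditional: it exists only if participation during follow-up is used, and the plan does not say that it is. Most of the other covariates read naturally as baseline characteristics. The baseline questionnaire is not reproduced and was adapted for this study, so an item on Cure Club may be in it. Care-giving responsibilities carry no date either, so a missing date alone does not make a covariate post-randomisation. Cure Club is a hospital support group, and prior attendance or attendance by usual-care participants is not excluded. The monthly logs are meant to define usual care and intervention dose, not to supply covariates.

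On size, no stated hypothesis test is touched, and a shift of 2–3% is small beside sampling error. With 100 per arm at 60% and 40%, the standard error of the log odds ratio is √(1/60 + 1/40 + 1/40 + 1/60) = 0.289, so the 95% interval around 2.25 runs from about 1.28 to 3.96. On this view, stating the time of measurement is enough.

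Most of this stands as a limit on the concern. It does not remove it. Care-giving has no described link to allocation, whereas the only described route into Cure Club is the intervention itself. Because the shift can go either way, it cannot be called conservative. An undated term also leaves the coding to be chosen once the data are in hand. Stating a date would not be enough if the date fell during follow-up.

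**Conclusion.** The concern holds. Both models include a covariate whose only described context is a possible consequence of allocation, and no time of measurement rules that reading out. If follow-up participation is used, neither adjusted estimate is the total effect of the intervention.

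The size cannot be derived from the documents. Under the assumptions shown, it is about 2–3% at 10% uptake. At 25% uptake it is about 12–17% in either direction for the odds ratio. For the hazard ratio at 25% it is about 6–7% downward (2.13–2.16 to 2.00) or 10–12% upward (2.00 to 2.21–2.24). If participation is a pre-randomisation item with similar uptake in both arms, the problem disappears.

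The primary z-test, the Kaplan-Meier and log-rank comparison and the sample size are not affected. This is a worthwhile correction to one secondary and one exploratory estimate, and no threat to the main conclusion.

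A separate limitation remains. The Sample Size Justification says: "For Phase 2, participants with successful linkage to clinical care from Phase 1" will be included. If the Cox model is confined to them, its hazard ratio is already conditioned on a post-randomisation event, and the change below does not cure that.

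**What to change.** In Section 7, under Secondary Outcome and Exploratory Analysis, remove Cure Club participation from the covariate lists of the models that estimate the intervention effect. Alternatively, restrict it to participation before randomisation, recorded at the baseline visit. The second option keeps a genuine baseline item if the questionnaire has one.

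Report participation after randomisation by arm as a measure of uptake, for example alongside the monthly activity logs. Label any Aim 3 model that includes it as descriptive.

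The cost is one deleted or dated term in two models, with no extra data, visits or participants. The sample size stays as planned.

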### **Sample Size Justification:**

Currently, 40% of new Viral Hepatitis Clinic appointments are attended by patients. Based on prior studies testing the intervention components in similar populations, including persons living with HIV and/or substance use disorders, it is expected that the intervention will improve the primary outcome of linkage to care by 18-30%. Although the effect size is not known in the context of HCV, we estimate an improvement in linkage of 20% (i.e., 60% attendance [0.60] in the NCM group compared to 40% attendance [0.40] in the usual care group) based on these prior studies. Using these figures and a two-tailed test with an alpha of 0.05, a conservative estimate of the total sample size required to achieve 80% power is 97 per group, or a total of 194 participants (G\*Power 3.1.9.2). With a sample size of 100 participants in each group, there should be an adequate number of participants to detect a difference in proportion of linkage to care for the primary aim.

For Phase 2, participants with successful linkage to clinical care from Phase 1 (those who attend  $\geq 1$  appointment at the Viral Hepatitis Clinic within 60 days) will be included. Therefore, the eligible sample size will be less than 40-60% of the original sample size because a linkage to care proportion of 0.40-0.60 is expected, and some participants will link to a clinical trial and not be included in this outcome. This is a secondary outcome and estimated effect size is unknown. However, with 100 participants in this group (half of the total sample size), we will have 90% power to detect a hazard ratio of 2.

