### 3. Background

Linkage to HCV care among people co-infected with HIV/HCV is poor. The greatest gap in the United States HCV care cascade begins between diagnosis and linkage to care. Only 25% of PLWH with chronic HCV have attended an HCV appointment, and less than half of those have ever initiated HCV treatment. A large cohort study in Baltimore found that only 21% of injection drug users with HCV had ever seen an HCV specialist. At the Johns Hopkins Moore Clinic, less than half of patients who are referred to an HCV specialist by their primary care provider actually attend the scheduled specialty appointment.

The perceived threat of HCV and perceived need for HCV care among patients is low. This perception, coupled with the fact that HCV is a “silent epidemic”, places PLWH at great risk. Qualitative studies describe that the absence of HCV-related symptoms leads to little interest in receiving HCV treatment. This is exacerbated by a lack of knowledge about HCV and available therapies; horror stories about interferon-related side effects and old ineffective treatments dominate conversations among peers with HCV despite these barriers being minimized with new all-oral therapy. People with HCV also report low motivation to engage in HCV care due to competing demands from work, school or caregiving responsibilities. Therefore, interventions to increase HCV knowledge and motivation, such as education, patient navigation, and appointment reminders are needed to improve linkage to HCV care.

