## **Enrollment**

**Patient Population/Setting:** The Bartlett Specialty Practice (formerly the Moore Clinic for HIV Care) at the Johns Hopkins Hospital provides HIV primary care to approximately 3500 men and women over the age of 18 per year. The clinic serves a primarily adult, urban population, with approximately 80% of patients being African American. The average age of clinic patients is 49 years. Approximately 50% of patients with HIV are co-infected with HCV. In Maryland, HCV therapy currently must be managed by a hepatology, gastroenterology, or infectious disease specialist for Medicaid reimbursement. The Viral Hepatitis Specialty Clinic, staffed with hepatologists and hepatitis-focused infectious disease physicians and nurse practitioners, is located within the Bartlett Specialty Practice. As of May 2015, 480 HIV/HCV co-infected patients at the Moore Clinic had *never* attended an appointment at the Viral Hepatitis Clinic; 90 patients never went to their scheduled appointments and 390 patients had never been scheduled for HCV care. In addition, a number of patients have not attended an appointment at the Viral Hepatitis Clinic in the era of all-oral therapy (including the past year). The median time between referral and available new patient appointment at the Viral Hepatitis Clinic is one week.

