**Enhanced Usual Care:** After randomization into the enhanced usual care arm, the nurse case manager will provide participants with the CDC HCV Fact Sheet and phone number for the CFAR Research Study Hotline. Participants will then be referred to the usual clinic appointment check-out process. To check-out of Bartlett Specialty Practice appointments, participants return to the front desk with a paper billing page and printed appointment referrals if applicable. The administrative staff closes the appointment encounter and gives the patient the phone number for the Johns Hopkins Hospital central scheduling phone line to schedule referral-based appointments. Patients are responsible for calling central scheduling to set up the specialty appointment. If an appointment is scheduled, all patients receive an automated appointment reminder call 2 days before the scheduled appointment from Johns Hopkins Hospital. Patients at the Bartlett Specialty Practice have access to nurse case managers and social workers assigned by their primary providers. Participants in the enhanced usual care arm will continue to have usual access to these services. Per the Bartlett Specialty Practice standard care protocol, once a prescription is written for HCV treatment, the assigned nurse case manager will work with the patient to coordinate HCV care; however, HIV nurse case managers are not directly involved in HCV care until after prescription for HCV treatment is written, which is the gap the proposed study seeks to fill.

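### The 40% usual-care linkage rate is attendance per appointment, not per randomised participant; this does not show low primary power, but it undercuts the Phase 2 size and its 90% power claim

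*Combined protocol and SAP*

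**What the plan says.** Section 7, Sample Size Justification, opens with "Currently, 40% of new Viral Hepatitis Clinic appointments are attended by patients". It then plans on "60% attendance [0.60] in the NCM group compared to 40% attendance [0.40] in the usual care group", using "a two-tailed test with an alpha of 0.05", and concludes that the "total sample size required to achieve 80% power is 97 per group, or a total of 194 participants". The trial enrols 100 per group.

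The primary outcome in section 7 is attendance at the Viral Hepatitis Center, in clinical care or an HCV-treating trial, within 60 days of randomisation. It is a yes/no result for each participant, analysed by intention-to-treat. A participant with no registered appointment is treated as a non-attender.

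Three other places bear on the rate:
- Section 4, Enrollment, describes 480 co-infected patients who had never attended: "90 patients never went to their scheduled appointments and 390 patients had never been scheduled for HCV care". It adds an uncounted group with no attendance in the all-oral era.
- Section 4, Enhanced Usual Care, says of booking: "Patients are responsible for calling central scheduling to set up the specialty appointment". In Phase 1 of the intervention, by contrast, the nurse telephones scheduling together with the participant during the visit.
- Section 3, Background, says that "less than half of patients who are referred to an HCV specialist by their primary care provider actually attend the scheduled specialty appointment". This figure also presupposes an appointment.

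For Phase 2, the Sample Size Justification says the eligible group will be less than 40-60% of the sample "because a linkage to care proportion of 0.40-0.60 is expected", and because some participants will link to a clinical trial and drop out of this outcome. It then claims 90% power for a hazard ratio of 2 with 100 participants.

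**The concern.** The 40% has appointments as its denominator. The endpoint has randomised participants as its denominator, including those who never obtain an appointment, and these are the people the 40% leaves out. Nothing in the documents converts one rate into the other or argues that they are equal.

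The gap matters because getting scheduled is one of the barriers the trial sets out to remove, and controls face it alone. A planning rate that takes an appointment as given assumes the barrier away in the control arm.

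Two planning statements depend on the rate: the 80% power for the primary comparison, and the number of linked participants available for the time-to-treatment comparison in Phase 2.

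**Working it through.** **1. The plan's own figure.** Inputs from the Sample Size Justification: control 0.40, intervention 0.60, two-sided alpha 0.05, power 80%. With the pooled two-proportion z-test:

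n = [1.96 × √(2 × 0.5 × 0.5) + 0.8416 × √(0.24 + 0.24)]² / 0.20² = (1.386 + 0.583)² / 0.04 = 96.9, so 97 per group.

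This reproduces the stated 97. The arithmetic is right; the question is the 0.40 that goes in.

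**2. How far 0.40 is supported.** Of the never-attended pool, 390/480 = 81% had never been scheduled and 90/480 = 19% had been scheduled without attending. The documents do not say what share of usual-care participants would obtain an appointment within 60 days. The control rates below 0.40 used here are therefore illustrations, not estimates.

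**3. Primary power at 100 per arm.** Power = Φ{[Δ − 1.96 × √(2p̄(1 − p̄)/100)] / √[(p₁(1 − p₁) + p₂(1 − p₂))/100]}, where p̄ is the mean of the two rates and Δ their difference.

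| Control vs intervention | Calculation | Power |
|---|---|---|
| 0.40 vs 0.60 (plan) | (0.20 − 0.1386)/0.0693 = 0.886 | 81% |
| 0.20 vs 0.40 | (0.20 − 0.1270)/0.0632 = 1.154 | 88% |
| 0.10 vs 0.40 | (0.30 − 0.1200)/0.0574 = 3.13 | above 99% |
| 0.20 vs 0.36 (odds ratio held at 2.25) | same formula | 72% |
| 0.20 vs 0.30 (ratio held at 1.5) | same formula | 37% |

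With the 20-point gain kept, a lower control rate raises power. Power drops below 80% only in the last two rows, where the absolute gain has shrunk to 16 and 10 points.

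**4. Phase 2 events.** By Schoenfeld's formula with an equal split, a hazard ratio of 2 at 90% power needs 4 × (1.960 + 1.282)² / (ln 2)² = 4 × 10.51 / 0.4805 = 87.5, so 88 treatment starts. The plan's 100 is 100 × 0.40 + 100 × 0.60, before removing those who link to a trial. So 90% power requires at least 88 of 100 linked participants to start treatment within 6 months, even on the plan's own rates.

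**5. Phase 2 at other linkage rates.** Linked number L = 100 × (control rate + intervention rate). As an upper bound, suppose every linked participant starts treatment. Then power = Φ{√[L × a(1 − a)] × ln 2 − 1.96}, where a is the control share of the linked group.

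| Linked, control vs intervention | L | a | Calculation | Upper bound on power |
|---|---|---|---|---|
| 40% vs 60% (plan) | 100 | 0.40 | √24 × 0.693 − 1.96 = 1.44 | 92% |
| 20% vs 40% | 60 | 0.33 | √13.3 × 0.693 − 1.96 = 0.57 | 72% |
| 20% vs 60% | 80 | 0.25 | √15 × 0.693 − 1.96 = 0.72 | 77% |

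All three rows are before removal of those who link to a clinical trial. They are upper bounds because the plan itself foresees decisions to defer treatment, a state fibrosis threshold for treatment, and censoring at 6 months.

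**The case against.** The strongest reply is that a lower control rate does the primary comparison no harm. The plan states its effect as 0.60 against 0.40, a 20-point gain, and on that scale 0.40 vs 0.60 gives the lowest power among the control rates considered. The low figures (72% and 37%) need an intervention rate of 36% or 30%. If the nurse books an appointment for nearly everyone and 40% of appointments are kept, intervention linkage would already be about 40% before any benefit from education or reminders. This stands. A reader might infer that the trial is underpowered for its primary aim, and the documents do not support that.

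A reader might also take the control rate to be the share scheduled multiplied by 0.40. That does not hold either. The endpoint is any attendance in 60 days, and the median wait for a new appointment is one week, so a missed visit can be rebooked. With two independent chances (an assumption), attendance among those scheduled is 1 − 0.6² = 64%, and 62.5% scheduled would then give 40% linked. Attendance at an HCV-treating trial also counts. Controls receive a research hotline number, and the Phase 1 text on linkage can be read as nurse referral in both arms, although Table 1 marks nurse-initiated referral as intervention only.

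Nor is 81% the never-scheduled share of the whole eligible pool. It covers the never-attended patients as of May 2015. Anyone with no hepatitis visit in the past year is eligible, and participants are volunteers, some referred by their provider.

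Finally, Phase 2 is a secondary outcome whose effect size the plan calls unknown, and the plan already warns that the group will be smaller. That is fair, but the 90% figure is still attached to 100 participants, and no figure is given for the smaller group.

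**Conclusion.** The point holds in this form. The 0.40 is a per-appointment rate used as a per-participant rate, without a conversion or a reason to treat the two as equal. It could be too high, but the documents do not allow its true value to be calculated, and the influences listed above work in both directions.

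For the primary comparison the consequence is a poorly sourced planning rate, not a demonstrated loss of power. Power is 81% as planned, higher if the 20-point gain holds from a lower base, and below 80% only if the absolute gain shrinks.

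For Phase 2 the consequence is firmer. The 90% power claim needs about 88 starts from 100 participants, in a group that the same paragraph expects to be smaller. That tension exists even at a control rate of 0.40, and a lower control rate widens it: 60 to 80 participants and at most about 72% to 77% power in the two illustrations. Those figures assume control linkage of 20%, intervention linkage of 40% or 60%, a hazard ratio of 2, every linked participant starting treatment, and nobody removed for linking to a trial.

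**What to change.** In the Sample Size Justification:

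- Replace 0.40 with a directly estimated 60-day linkage proportion per eligible patient. Take eligible patients with an HIV clinic visit and count those who attended the Viral Hepatitis Center within 60 days, adding clinical-trial attendance confirmed with the trial coordinators. Do not derive it as the share scheduled times 0.40.
- Restate primary power at 100 per arm over a range of control rates, and say whether the effect is held constant as a difference, a ratio or an odds ratio. The range also covers the difference between clinic patients and consenting volunteers.
- Restate the expected Phase 2 number after removing those who link to a clinical trial. Give its power by the number of treatment starts expected within 6 months, in place of 90% with 100 participants.

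The sample size, endpoint and procedures stay as they are. The cost is one records query, for which the weekly review of clinic appointments already identifies the patients, confirmation of trial attendance, and a rewritten paragraph. The Phase 2 power statement will look less favourable.
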